### **8.3. Secondary Efficacy Analyses**

For the Final Analysis, the secondary efficacy endpoint, change from Baseline Hgb at Week 48 will be assessed in the same manner, using data for all visits up to and including the Week 48 visit, as described in section 8.2 for the Week 24 visit.

The 95% CI for the mean change from baseline will be obtained for each of the following secondary efficacy endpoints by using an MMRM:

1. Change in transferrin saturation (TSAT) from Baseline at Weeks 24 and 48
2. Change in ferritin from Baseline at Weeks 24 and 48
3. Change in serum phosphate from Baseline at Weeks 24 and 48
4. Change in eGFR from Baseline to Weeks 24 and 48
5. Change in bicarbonate from Baseline to Weeks 24 and 48

The same type statistics as described in Section 8.2 for Hgb will also be provided for the endpoints listed above where the change from Baseline to Week 24 results and the change from Baseline to Week 48 results will be presented in tables for the 24-Week analysis and the Final analysis, respectively.

Ninety-five percent CIs will be constructed for mean change from Baseline Hgb at Week 24 and mean change from Baseline Hgb at Week 48 based on the data for the PP analysis subjects who complete their Week 24 visit and data for the PP analysis subjects who complete their Week 48

visit, respectively, by starting dose treatment group and these two groups combined. The parametric analysis of covariance (ANCOVA) model for change from baseline in Hgb at Week 24 and at Week 48 with an intercept term, baseline Hgb as a covariate, starting dose treatment group effect, and a random error will be used to obtain the least squares mean (LSM), the associated standard error and associated 95% confidence intervals. To check the model assumption regarding normality for residuals and to detect potential outliers a normal probability plot of residuals and a plot of the residuals versus the fitted values will be used. If necessary, transformations and/or dropping of outliers to obtain data that meet these assumptions will be implemented.

Intact parathyroid hormone (iPTH), C-terminal fibroblast growth factor 23 and intact fibroblast growth factor 23 are only measured at Randomization Day, Week 24 and Week 48. Therefore, the type of ANCOVA model as described above for change for Baseline Hgb in the PP/mPP analysis subjects who complete the Week 24 visit and those who complete the Week 48 visit will be used to obtain the 95% confidence intervals for the means of the following:

1. Change in intact parathyroid hormone (iPTH) from Baseline to Weeks 24 and 48
2. Change in C-terminal fibroblast growth factor 23 from Baseline to Weeks 24 and 48
3. Change in intact fibroblast growth factor 23 from Baseline to Weeks 24 and 48.

Box plots over time of the observed value and the change from Baseline for each of the efficacy parameters, Hgb, TSAT, ferritin and serum phosphate will be provided. The box plots will be constructed based on observations made during the window of time designated for each visit given in section 6.5.4. If there are visits that are out of window, a scatter plot of the in-window and out of window observations will be used along with the box plots to explore the question of the stability of Hgb, TSAT, ferritin and serum phosphate during treatment with the study medication.

The Kaplan-Meier estimator of the survival function of time from randomization to first increase from Baseline Hgb of at least 0.5 g/dL for each of the two starting dose treatment groups will be obtained. The Kaplan-Meier plot of the functions for the two starting doses will be presented on a single figure.

A table will be presented that shows for the PP/mPP analysis set by treatment group the following for the event, time from randomization to first increase from Baseline Hgb of at least 0.5 g/dL, during the Dose Titration Period:

- Estimated median time in days;
- Number and percentage of subjects who had at least one event;

- Number and percentage of subjects with time to the event censored (Censoring occurs if a subject does not have the event prior to either completing the Week 24 visit or discontinuing from the study prior to the Week 24 visit.).

Tables displaying descriptive statistics will be provided for the Week 24 analysis and the Final analysis for the following secondary efficacy endpoints:

- Change in FACIT Fatigue Scale from Baseline at Weeks 24 and 48;
- Change in WPAI questionnaire specific health problem score from Baseline at Weeks 24 and 48

where the change from Baseline at Week 24 results and the change from Baseline at Week 48 results will be presented in tables for the 24-Week analysis and the Final analysis, respectively.

Descriptive statistics will also be provided for the number of hospitalizations and duration of hospital stay in days during the Dose Titration Period and the entire study for the 24-Week Analysis and Final Analysis, respectively.

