8.3. Subject Withdrawal Criteria

8.3.1. Discontinuation From Study Drug

Discontinuation from study drug is defined as a permanent termination of treatment with KRX-0502. Subjects may be discontinued from the study drug at any time for any of the following reasons:

- Adverse event
- Lack of efficacy (see [Section 9.2.2](#))
- Pregnancy
- Withdrawal by subject
- Other

If at any time during the course of the study, in the opinion of the Investigator, the subject may no longer safely participate due to a change in medical status (eg, experiences an AE, becomes pregnant), the subject must be discontinued from the study drug.

Whenever study drug is discontinued prematurely, Keryx and the Medical Monitor must be notified. The subject should return for the ET visit and exit the study.

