### 4.3. Sample Size Considerations

#### 4.3.1. Sample Size Justifications

Because this is an open-label Phase 4 study designed to estimate within-group changes from Baseline and describe time trends of iron parameters in subgroups of subjects, it is appropriate to conduct a precision-based sample size estimation as opposed to a power-based calculation. The primary endpoint of interest is change in Hgb from Baseline at Week 24. The standard deviation

(SD) for that endpoint is estimated as 0.9 g/dL based on the Week 16 data in a prior Phase 3 study in a similar population (Keryx Study KRX-0502-306).

Assuming a population SD of 0.9 g/dL, with a sample size of 140 subjects, the 95% confidence intervals (CIs) for mean change in Hgb from Baseline to Week 24 can be estimated, allowing for a CI half-width of 0.149 g/dL.

It is assumed that 30% of the subjects in this study will drop out or be otherwise excluded from the PP population. Hence, 200 subjects will be randomized to ensure that there will be sufficient subjects at the end of the study for the longitudinal analyses (i.e., 70 evaluable subjects in each randomized treatment group). Based on prior clinical trial experience, it is estimated that half of the subjects will stay on their starting dose, and the other half will increase their dose after 12 weeks of treatment. Hence, it is expected that the 4 dosing sequence groups that will arise will have approximately equal numbers of subjects (i.e., 35 subjects are expected in each of the four dosing sequence groups (3-3, 3-6, 4-4, and 4-6 tablets/day).

The proposed sample size and the sizes of the subgroups of interest are deemed sufficient for the analyses proposed below including the longitudinal analyses.

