#### **4.5. Clinical Assessments**

The complete schedule of assessments for this study is presented in Table 2 of the protocol.

Data from the central laboratory will be used for efficacy and safety analyses including analyses for supportive and exploratory endpoints. The following laboratory evaluations will be performed at the central laboratory:

- A complete blood count (CBC); including white blood cell (WBC), white blood cell types (WBC differential), red blood cell (RBC) count, hematocrit (HCT), Hgb, RBC indices and platelet (thrombocyte) count will be performed at Visit 1A (Screening) and, if applicable, Visit 1B (Re-screening); Visit 2 (Randomization); and all subsequent visits.

- A complete chemistry profile (CCP); including sodium, potassium, phosphorus, calcium, calcium adjusted for albumin, chloride, carbon dioxide/bicarbonate, glucose, blood urea nitrogen [BUN], creatinine, estimated glomerular filtration rate (eGFR) based on the Modification of Diet in Renal Disease (MDRD) Study equation, aspartate aminotransferase [AST], alanine aminotransferase [ALT], alkaline phosphatase [ALP], total bilirubin, total protein, and albumin) will be performed at Visit 1A (Screening) and, if applicable, Visit 1B (Re-screening); Visit 2 (Randomization); and all subsequent visits.
- Iron studies (TSAT, ferritin, transferrin, unsaturated iron-binding capacity [UIBC], total iron-binding capacity [TIBC] and serum iron) will be performed at Visit 1A (Screening) and Visit 1B (Re-screening), if applicable, Visit 2 (Randomization); and all subsequent visits.
- FGF23 (intact and C-terminal) testing will be performed at Visit 2 (Randomization), Visit 9 (Week 24), Visit 12 (Week 48), and the Early Termination (ET) visit.
- Intact parathyroid hormone (iPTH) testing will be performed at Visit 1A (Screening) and if applicable, Visit 1B (Re-screening); Visit 2 (Randomization); Visit 9 (Week 24); Visit 12 (Week 48); and the ET visit.

The laboratory parameters used in the assessment of efficacy are:

- Hgb,
- TSAT,
- Ferritin and
- Serum phosphate

The schedule for the additional efficacy assessments is as follows:

- Work Productivity and Activity Impairment (WPAI) Questionnaire and FACIT Fatigue Scale Questionnaire will be administered at Visit 2 (Randomization); Visit 9 (Week 24); Visit 12 (Week 48); and the ET visit.
- Number of hospitalizations and duration (days) will be assessed at each visit.

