## **6.6. Handling of Missing Data**

### **6.6.1. Missing Efficacy Endpoints**

Subjects who discontinue will not be replaced. If efficacy endpoint data are missing, they will not be imputed.

Mixed models will be used to analyze the repeated measures data for visits up to and including Week 24 and Week 48. The Mixed Model Repeated Measures (MMRM) models described in section 8.2 implicitly adjust for missing data under the assumption of missing at random.

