**Table 3: Analysis Method and Analysis Set for Special Focus Efficacy Endpoints**

Efficacy Parameter	24-Week Analysis (Study Period: Dose Titration Period)	Final Analysis (Study Period: Entire Study)	Analysis Method	Analysis Set
Hgb	Change from Baseline to Week 24*	Change from Baseline to Week 48	MMRM	PP 
Hgb	Change from Baseline at Week 24	Change from Baseline at Week 48	ANCOVA	PP  Completers
Hgb	Time from Randomization to First Increase from Baseline Hgb >= 0.5 g/dL	Not Applicable	Kaplan-Meier	PP 
TSAT, ferritin, phosphate, bicarbonate, eGFR	Change from Baseline to Week 24	Change from Baseline to Week 48	MMRM	PP 
PTH, c-terminal and intact FGF-23	Change from Baseline to Week 24	Change from Baseline to Week 48	ANCOVA	PP 
FACIT score	Change from baseline at Week 24	Change from Baseline to Week 48	Descriptive	PP 
WPAI	Change from Baseline to Week 24	Change from Baseline to Week 48	Descriptive	PP 
Hospitalizations	Number and Duration ( days)	Number and Duration ( days)	Descriptive	PP 

Hgb, TSAT, ferritin, phosphate	Change from Baseline to Week 24	Change from Baseline to Week 48  Change from Baseline to Week 24	MMRM	FAS subjects who received permitted ESA Rescue Therapy
Hgb, TSAT, ferritin, phosphate		Change from Baseline to Week 48  Change from Baseline to Week 24	MMRM	PP Dosing sequence groups

\* Hgb change from baseline to Week 24 is the primary endpoint.

The analysis set used will either be the modified PP Analysis Set (24-Week Analysis snapshot) or PP Analysis Set (24-Week and Final Analysis).

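### The Week 48 iPTH and FGF23 estimates use Week 48 completers only, so the Week 24 values of PP subjects who leave later do not inform them, and SAP 8.3 and Table 3 name different analysis sets

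*SAP*

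**What the plan says.** - **Method and population.** SAP 8.3 notes that the three markers "are only measured at Randomization Day, Week 24 and Week 48" and concludes that the Hgb-type ANCOVA "in the PP/mPP analysis subjects who complete the Week 24 visit and those who complete the Week 48 visit will be used". The Hgb model is specified "with an intercept term, baseline Hgb as a covariate, starting dose treatment group effect, and a random error will be used". I read this as using each marker's own baseline in its own model. No Week 24 value enters the Week 48 model.
- **Table 3.** The row "PTH, c-terminal and intact FGF-23" is assigned ANCOVA with set PP. The Hgb ANCOVA row is labelled PP Completers.
- **Missing data.** SAP 6.6.1 rules out imputation of efficacy endpoints.
- **Early Termination samples.** SAP 4.5 states: "FGF23 (intact and C-terminal) testing will be performed at Visit 2 (Randomization), Visit 9 (Week 24), Visit 12 (Week 48), and the Early Termination (ET)". The same schedule applies to iPTH, and Protocol 13.1.4.4 agrees. Under SAP Table 2, footnote c, an ET visit takes the name of the window it falls in: Days 198-253 are Week 32, Days 254-309 are Week 40, and anything after Day 309 is Week 48.
- **Exit rule.** Protocol 8.3.1 says of anyone who stops study drug early: "The subject should return for the ET visit and exit the study".
- **Planned loss.** SAP 4.3.1: "It is assumed that 30% of the subjects in this study will drop out or be otherwise excluded from the PP population".

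**The concern.** The step from few visits to visit-wise ANCOVA does not follow. Two post-baseline visits are already repeated measures, and the Section 8.2 model can be fitted to them. Hgb, TSAT, ferritin, phosphate, eGFR and bicarbonate all get that model. eGFR and bicarbonate were also added as secondary endpoints in the SAP, so endpoint rank does not explain the difference.

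For Hgb the completer ANCOVA sits beside an MMRM. For these three markers it is the only planned inferential analysis, and SAP 9.6 removes multiple imputation and the general FAS efficacy analyses.

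Stopping drug leads to study exit, and Protocol 8.3.2 lists start of chronic dialysis or transplantation among the reasons for leaving. If marker levels are related to who leaves between Weeks 24 and 48, the reported Week 48 mean change and CI describe those who stayed, while Table 3 tells the reader that they describe PP.

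**Working it through.** **1. The plan's own figure.** 1.96 × 0.9/√140 = 0.149 g/dL and 140/(1 − 0.30) = 200. Both reproduce SAP 4.3.1. They concern Hgb and do not size this point. I take only n = 140 from them, and work in SD units of the Week 48 change adjusted for baseline: SE = 1/√140 = 0.085 SD, CI half-width = 1.96 × 0.085 = 0.166 SD, and SE per arm (n = 70) = 0.120 SD.

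**2. Which leavers have a Week 48 value.** Days 198-309 span 309 − 198 + 1 = 112 days. From Day 198 to the Week 48 target, Day 337, is 140 days. So 112/140 = 80% of that interval yields an ET sample named Week 32 or Week 40. From Day 310 the sample is named Week 48. 8.3 does not say whether a subject with such a sample has completed the Week 48 visit.

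**3. Bias formula.** Let f be the share of subjects with a Week 24 value who lack a Week 48 value, ρ the correlation of the adjusted Week 24 and Week 48 changes, and δ the leaver-minus-stayer difference at Week 24 in SD. The stayers' Week 24 mean is off by fδ. If leaving depends only on what was seen by Week 24 (missing at random, MAR), the completers' Week 48 mean is off by fρδ. The large-sample ratio of the two-visit SE to the completer SE is √(1 − fρ²).

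**4. Numbers.** The documents give no value for f, ρ or δ, so all inputs here are assumed.

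| Assumptions | Size of bias (SD) | Reduction in SE |
|---|---|---|
| f 10-20%, ρ 0.5-0.8, δ 0.3-1.0 | 0.10×0.5×0.3 = 0.015 to 0.20×0.8×1.0 = 0.16 | 1 − √0.975 = 1.3% to 1 − √0.872 = 6.6% |
| f 5-30%, ρ 0.3-0.7, odds of leaving ×1.5 to ×2.0 per SD of the Week 24 residual | 0.006 to 0.133 | 1 − √0.9955 = 0.2% to 1 − √0.853 = 7.6% |

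A middle case in the second set (f = 15%, ρ = 0.5, odds ratio 2) gives 0.049 SD, which is 0.049/0.166 = 0.30 of the pooled half-width. The largest value, 0.16 SD, is about the whole half-width (0.16/0.085 = 1.9 SE pooled; 0.16/0.120 = 1.3 SE per arm).

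**5. Simulation check** (4,000 runs per setting, about 140 completers, odds ratio 2). At f = 15%, ρ = 0.5 the completer ANCOVA was off by 0.048 SD and the two-visit model by 0.001 SD. In every setting the two-visit bias was at most 0.002 SD. The simulated precision gain was smaller than the formula suggests: at f = 30%, ρ = 0.7 the SE went from 0.085 to 0.081, and in the other settings there was little or no change.

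**The case against.** Several stronger readings are tempting, and the documents do not support them.

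- **That everyone who leaves after Week 24 is dropped.** ET samples are scheduled for these markers, and one taken after Day 309 is labelled Week 48. The SAP is silent on its use, which is a gap and not an exclusion.
- **That leavers are discarded altogether.** They remain in PP, and their Week 24 values enter the Week 24 ANCOVA.
- **That SAP 6.6.1 already requires a mixed model here.** It says "Mixed models will be used to analyze the repeated measures data for visits up to and including Week 24 and Week 48", but goes on to identify these as the models of Section 8.2. SAP 5.1 and Table 3 expressly assign ANCOVA to these markers.
- **That the planned 30% fixes the loss**, for example about 16% in each half of the study at a constant exit rate (1 − √0.7 = 0.163). The 30% also covers exclusions from PP, which affect both methods alike, and it is not split by period.

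It is also fair to say that a single-visit ANCOVA can use only subjects with a value at that visit, so the PP versus completers mismatch is partly one of labels. The endpoints are secondary, were added in the SAP, and are estimated by CI with no decision rule. The MMRM removes the bias only under MAR, which is least secure for exits to dialysis or transplantation months after the Week 24 sample. ET samples from Days 198-309 stay unused in a two-visit model as well.

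These points limit the size and priority of the concern. They do not change the fact that the Week 48 estimate ignores Week 24 data already in hand.

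**Conclusion.** The point holds in limited form. The Week 48 iPTH and FGF23 estimates rest on Week 48 completers, make no use of later leavers' Week 24 values, and carry a different set label in Table 3. The status of an ET sample named Week 48 is undefined. The Week 24 estimates are not affected.

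The size cannot be derived from the documents. Over the two assumed sets above, the bias runs from about 0.01 to 0.16 SD with unknown direction, and the gain in SE from under 1% to about 8%. The case for change is the avoidable bias under MAR; the precision gain is small. This is a low-cost improvement to secondary endpoints and does not touch the primary analysis.

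**What to change.** For the Final Analysis only:

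1. In SAP 8.3, analyse each of the three markers with the Section 8.2 MMRM on Weeks 24 and 48: marker baseline, starting dose group, visit, group-by-visit, baseline-by-visit, unstructured 2×2 covariance, Kenward-Roger. Include every PP subject with at least one Week 24 or Week 48 value. Report the Week 48 LS mean and CI from this model, and keep the completer ANCOVA as supportive.
2. State in 8.3 that an ET value windowed to Week 48 under Table 2, footnote c, is used.
3. Split the Table 3 row so that only its Final Analysis entry becomes MMRM with set PP.

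Leave the 24-Week analysis and the snapshot as ANCOVA. With one post-baseline visit the MMRM reduces to the same model, and SAP 5.1 specifies ANCOVA for the snapshot.

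The cost is SAP wording and a rerun of the existing PROC MIXED program for three more parameters, with no new data. The price in assumptions is reliance on MAR, which the SAP already accepts for Hgb, and which should be acknowledged as doubtful for exits due to dialysis or transplantation.

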8.3.2. Discontinuation From Study

Subjects may discontinue from the study for the following reasons:

- Discontinuation from study drug (see Section 8.3.1)
- Subject withdrawal of consent
- Lost to follow-up
- Study drug non-compliance
- Investigator judgment
- Use of certain prohibited therapies (see [Section 9.2.1](#) and [Section 9.2.2](#))
- Start of chronic dialysis or kidney transplantation
- Death
- Sponsor termination of study
- Other

The Investigator should inquire about the reason for withdrawal, request the subject to return all unused investigational product, request the subject to return for a final ET Visit as soon as possible to undergo the assessments specified for the visit, and follow-up with the subject regarding any unresolved AEs. For ETs that occur on or after the day of study drug initiation, every effort should be made to document the subject's outcome, regardless of cause. Whenever a subject is discontinued prematurely, Keryx and the Medical Monitor must be notified.

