9.2.2. ESA Rescue Therapy

ESA use is not permitted during the study. The exception is a scenario in which all of the following conditions for ESA rescue therapy are met:

1. A subject has had 2 consecutive Hgb values of <8.0 g/dL more than 3 days apart.
2. The Investigator decides to treat the subject with ESA as per standard of care.
3. The Investigator deems it appropriate for the subject to continue in the study.
4. The subject continues in the study on study drug.

Any subject who is to receive or has received ESA therapy regardless of whether its use constitutes permitted ESA rescue therapy or not should be discussed with the Medical Monitor as soon as possible to decide whether the subject may remain in the study.

Subjects who received ESA during the study and who remain in the study will be excluded from the PP analysis set. Subgroup analyses will be conducted for these subjects.

Subjects who have had 2 consecutive Hgb values of <8.0 g/dL more than 3 days apart but do not meet the other criteria of ESA rescue therapy should complete the ET visit and discontinue from the study.

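### The Kaplan-Meier curve for a first Hgb rise of 0.5 g/dL censors every early exit alike, so 1-KM overstates the share who respond on each regimen; add a cumulative incidence estimate

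*SAP*

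**What the plan says.** SAP Table 3 lists "Time from Randomization to First Increase from Baseline Hgb >= 0.5 g/dL" among the special-focus endpoints, analysed by Kaplan-Meier in the PP set (mPP for the snapshot). SAP 9.6 records that the endpoint is not in the protocol. SAP 8.3 specifies "The Kaplan-Meier estimator of the survival function of time from randomization to first increase from Baseline Hgb of at least 0.5 g/dL" for each starting dose, with both curves on one figure. The accompanying table, which covers events "during the Dose Titration Period", gives the median, the "Number and percentage of subjects who had at least one event" and the number censored. The rule is: "Censoring occurs if a subject does not have the event prior to either completing the Week 24 visit or discontinuing from the study" ahead of Week 24. Exit reasons are not separated. The missing-at-random statement in SAP 6.6.1 concerns the MMRM only, and no sensitivity analysis is given for this endpoint.

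The protocol decides who exits:

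- 8.3.1, on permanent drug discontinuation: "The subject should return for the ET visit and exit the study".
- 8.3.2 lists death and "Start of chronic dialysis or kidney transplantation" as reasons for leaving.
- 9.2.2: subjects with two consecutive Hgb values below 8.0 g/dL who "do not meet the other criteria of ESA rescue therapy should complete the ET visit and discontinue from the study".

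**The concern.** Kaplan-Meier treats a censored subject as having the same future chance of the event as those still under observation. That is reasonable for administrative censoring. It is not reasonable for someone who has died, started dialysis, stopped drug for intolerance, or left because Hgb fell below 8.0 g/dL. The last is a failure of the very quantity being timed.

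The complement of the curve then answers a hypothetical question: what share would respond if nobody left for these reasons. Protocol 6.2 says the study should inform real-world management, where stopping is part of how a regimen performs. A reader who takes the curve as the proportion responding by a given week gets a figure that is too high.

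**Working it through.** **The plan's own figures.** Protocol 15.2 gives a half-width of 0.149 g/dL: 1.96 × 0.9/√140 = 0.149, and 140/(1 − 0.30) = 200 randomized. Both reproduce. No rate, median or precision is stated for the time-to-event endpoint, so everything below rests on assumed rates.

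**Inputs.**

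- Response: half by Week 12, constant hazard h = ln 2/12 = 0.0578 per week. This is a proxy. Protocol 15.2 expects half to keep their starting dose, but that requires a rise of at least 0.5 g/dL and also Hgb of at least 10 g/dL at Week 12.
- Loss L over 48 weeks, constant hazard g = −ln(1 − L)/48. For L = 30%, g = 0.00743 and loss by Week 24 is 1 − √0.70 = 16.3%. For 20% it is 10.6%, and for 10% it is 5.1%.
- Share of exits that are competing: half, three quarters or all. The documents give no split.

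**Continuous-time check, L = 30%, all exits competing.** 1-KM at Week 24 is 1 − exp(−24h) = 75.0%. Cumulative incidence is h/(h+g) × [1 − exp(−24(h+g))] = 0.886 × [1 − exp(−1.565)] = 70.1%, a gap of 4.9 points. The median is 12.0 weeks by Kaplan-Meier and −ln(1 − 0.5/0.886)/(h+g) = 12.7 weeks by cumulative incidence.

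**With Hgb read at Weeks 2, 4, 8, 12, 16, 20 and 24.** In each interval of d weeks, competing exits remove a fraction 1 − exp(−s·g·d) of those at risk (s is the competing share). A fraction 1 − exp(−h·d) of the remainder then respond at the visit. 1-KM stays at 75.0%. The excess over cumulative incidence at Week 24, in points, is:

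| Loss over 48 weeks | Half competing | Three quarters | All |
|---|---|---|---|
| 10% | 0.9 | 1.4 | 1.8 |
| 20% | 1.9 | 2.8 | 3.7 |
| 30% | 3.0 | 4.4 | 5.8 |

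For scale, the standard error of a 75% proportion with 70 subjects is √(0.75 × 0.25/70) = 5.2 points. The 70 is already net of the 30% loss, so comparing the bottom row with it counts the loss twice.

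**Other response rates.** With 50-80% responding by Week 24 in the absence of exit, the gap is 1.3-1.8 points at 5% competing exit by Week 24, 2.6-3.6 at 10% and 4.0-5.5 at 15%.

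**Median.** In continuous time it moves by 0.7 weeks at most on the main inputs. Because Hgb is read only at visits, it can jump a whole visit when the curve crosses 50% close to one. The main inputs are such a case, since 1-KM is exactly 50% at Week 12. With 60% responding by Week 24 and 15% exit, the median goes from Week 20 to Week 24. With 50% responding by Week 24, the cumulative incidence never reaches 50%.

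**Count illustration.** Take 100 subjects with 10, 10, 12, 10, 6, 4 and 3 responses at the seven visits, and 1, 1, 3, 3, 3, 2 and 2 competing exits just before them. 55 respond. Kaplan-Meier gives 1 − (89/99 × 78/88 × 63/75 × 50/60 × 41/47 × 35/39 × 30/33) = 60.3%.

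**The case against.** The best reply is that the same table already carries an uninflated figure. If every exit is competing, the crude percentage with an event equals the cumulative incidence at Week 24. If some exits are ordinary censoring, the crude percentage is lower still. The only Kaplan-Meier number planned is the median, which moves little on the main inputs, and no percentage is planned at a fixed week. This stands, and it limits the harm. It does not correct the curve, which will disagree with the table with no explanation in the plan.

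The 30% also overstates exits in this analysis. It includes PP exclusions, and subjects given IV iron, red cell transfusion or any ESA are removed from PP and mPP rather than censored (SAP 6.3.5 and 6.3.6). Low compliance also removes subjects from PP. Lack of efficacy in Protocol 8.3.1 refers to 9.2.2, so it should not be counted as a separate route from the Hgb rule. All of this stands, and 5.8 points is a ceiling.

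A reader might infer that censored subjects cannot respond at all. That is literal only for death. After drug stop or dialysis, Hgb could still rise but would not be observed. Hgb is drawn at the ET visit (Protocol 10.6.2) and mapped to a visit window (SAP Table 2, note c), so a rise present at exit can still count. Censoring at drug stop also suits a hypothetical on-treatment question, but SAP 8.3 does not say that this is the question.

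**Conclusion.** The point holds for the curve and, to a lesser degree, the median. 1-KM cannot fall below cumulative incidence and exceeds it whenever a competing exit precedes later responses. On the stated assumptions the excess at Week 24 is about 1 to 4 points for 10-20% loss over 48 weeks. It reaches about 6 points only if the whole planned 30% were competing exits. The median changes little unless response is slower than assumed or the curve crosses 50% near a visit.

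A reader might also infer that the less well tolerated regimen is flattered relative to the other. That needs a difference in exit rates between starting doses, which the documents do not give. SAP 8.3 plans no between-group test for this endpoint. The endpoint is descriptive and secondary, and the primary result is untouched. The consequence is an optimistic picture of response, correctable at low cost.

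**What to change.** In SAP 8.3, beside the Kaplan-Meier figure, add the Aalen-Johansen cumulative incidence of response by starting dose, with 95% CIs at Weeks 12 and 24, and this mapping:

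- **Competing events:** death; start of dialysis or transplantation; drug or study discontinuation for an adverse event or pregnancy; two Hgb values below 8.0 g/dL without rescue; exit for prohibited therapy. Each applies only where the subject remains in the analysis set.
- **Censored:** loss to follow-up; withdrawal by the subject or of consent; administrative or sponsor termination; event-free at Week 24.
- **Where the study-exit reason is only that study drug was discontinued:** classify by the drug-discontinuation reason in SAP 7.1.2. This step is needed because subject withdrawal is itself one of those reasons.
- **Remaining SAP 7.1 categories** (non-compliance, investigator judgment, protocol violation, other): assign before database lock.

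Tabulate censored subjects by exit reason, and state that the Kaplan-Meier curve is not the proportion responding.

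The cost is a paragraph of SAP text, the mapping and one extra analysis from reasons already collected. The reported response will look slightly less favourable.
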